**REGENERON CONFIDENTIAL** 

Page 98 of 99

VV-RIM-00295189-1.0 Approved - 24 Mar 2023 GMT-5:00

$\Delta_{\text{FEV1_24_Dupi}}$	Mean absolute change from baseline in pre-bronchodilator FEV1 at Week 24 in the dupilumab group
$\Delta_{\text{FEV1_24_Pbo}}$	Mean absolute change from baseline in pre-bronchodilator FEV1 at Week 24 in the placebo group
AAS	Anti-drug Antibody Analysis Set
ABPA	Allergic bronchopulmonary aspergillosis
ACQ-5	Asthma Control Questionnaire 5-item version
ADA	American Diabetes Association
ADA	Anti-drug antibody
AE	Adverse event
AESI	Adverse event of special interest
A fumigatus	Aspergillus fumigatus
ALC	Absolute lymphocyte count
ALP	Alkaline phosphatase
ALT	Alanine aminotransferase
ANCA	Antineutrophil cytoplasmic antibodies
ANCOVA	Analysis of covariance
AST	Aspartate aminotransferase
ATC	Anatomical Therapeutic Chemical
ATS	American Thoracic Society
BDM	Biostatistics and Data Management
BMI	Body mass index
BUN	Blood urea nitrogen
CCG	Clinical completion guideline
██████████	██████████
CI	Confidence interval
CK	Creatine kinase
CMQ	Custom MedDRA® query
CPK	Creatine phosphokinase
CPMP	Committee for Proprietary Medicinal Products
CT	Computed tomography
DBP	Diastolic blood pressure
DILI	Drug-induced liver injury

ECG	Electrocardiography
eCRF	Electronic case report form
ED	Emergency department
EOS	End of study
EOT	End of treatment
ERS	European Respiratory Society
FAS	Full Analysis Set
FDA	Food and Drug Administration
[REDACTED]	[REDACTED]
FeNO	Fractional exhaled nitric oxide
FEV1	Forced expiratory volume in 1 second
[REDACTED]	[REDACTED]
Hb	Hemoglobin
HBcAb	Hepatitis B core antibody
HBsAb	Hepatitis B surface antigen antibody
HBsAg	Hepatitis B surface antigen
HCVAb	Hepatitis C virus antibody
HIV	Human immunodeficiency virus
HLT	High level term
HR	Heart rate
[REDACTED]	[REDACTED]
HRQoL	Health-related quality of life
HU	Hounsfield units
ICF	Informed consent/assent form
ICS	Inhaled corticosteroids
IFN- γ	Interferon gamma
IgE	Immunoglobulin E
IgG	Immunoglobulin G
IL4R	Interleukin-4 receptor
ISHAM	International Society for Human and Animal Mycology
IVRS	Interactive voice response system
IWRS	Interactive web response system
LABA	Long-acting beta agonist

LAMA	Long-acting muscarinic receptor antagonist
LDH	Lactate dehydrogenase
LLN	Lower limit of normal
LLOQ	Lower limit of quantification
LTRA	Leukotriene receptor antagonist
MAR	Missing at random
MCMC	Markov-chain Monte Carlo
MedDRA®	Medical Dictionary for Regulatory Activities
MMRM	Mixed-effects model with repeated measures
NAb	Neutralizing antibody
NAS	Neutralizing Antibody Analysis Set
OAF	Oral antifungals
OCS	Oral corticosteroids
OLS	Ordinary least squares
PCSV	Potentially clinically significant value
[REDACTED]	[REDACTED]
pH	Potential of hydrogen
PK	Pharmacokinetic
PKAS	Pharmacokinetic Analysis Set
PR	P wave, R wave
PRO	Patient-reported outcome
PT	Preferred term
Q1	First quartile
Q2W	Every 2 weeks
Q3	Third quartile
QRS	Q wave, R wave, S wave
QT	Q wave, T wave
QTcB	Corrected QT interval by Bazett's formula
QTcF	Corrected QT interval by Fredericia's formula
RBC	Red blood cells
Ref	Reference
REML	Restricted maximum likelihood
SABA	Short-acting bronchodilator

1. OVERVIEW

The statistical analysis plan (SAP) is intended to be a comprehensive and detailed description of the statistical methods, timing of analyses, and analysis presentation to be used for the study specified in protocol R668-ABPA-1923 amendment 4, dated March 24, 2023.

1.1. Study Description and Objectives

This is a phase 2, global, multicenter, randomized, double-blind, placebo-controlled, parallel-group study to evaluate the efficacy and safety of dupilumab in patients with allergic bronchopulmonary aspergillosis (ABPA) who meet modified International Society for Human and Animal Mycology (ISHAM) working group 2013 criteria for ABPA. Approximately 60 patients will be enrolled in the study and randomized in a 1:1 ratio to receive either dupilumab 300 mg subcutaneously (SC) every 2 weeks (Q2W) or placebo SC Q2W for a minimum of 24 weeks and a maximum of 52 weeks.

1.1.1. Primary Objectives

The primary objective of the study is to evaluate the efficacy of dupilumab on lung function in patients with ABPA.

1.1.2. Secondary Objectives

The secondary objectives of the study are:

- To evaluate the effects of dupilumab on exacerbations in patients with ABPA
- To evaluate the effects of dupilumab on ABPA-related exacerbations
- To evaluate the effects of dupilumab on hospitalization/emergency department (ED)/urgent care visits in patients with ABPA
- To evaluate the effects of dupilumab on asthma control in patients with ABPA
- To evaluate the effects of dupilumab on health-related quality of life (HRQoL) in patients with ABPA
- To evaluate the effects of dupilumab on serum total immunoglobulin E (IgE) and *Aspergillus*-specific IgE concentrations
- To evaluate the effects of dupilumab on fractional exhaled nitric oxide (FeNO) levels
- To evaluate safety and tolerability of dupilumab in patients with ABPA
- To evaluate dupilumab concentrations in serum and the incidence of anti-dupilumab antibodies in patients with ABPA

1.1.3. Exploratory Objectives

The exploratory objectives of the study are:

1.2. Statistical Hypothesis

The primary analyses of the study compare the treatment effect of dupilumab 300 mg Q2W against placebo on the absolute change from baseline in pre-bronchodilator forced expiratory volume in 1 second (FEV1).

The statistical hypotheses to test dupilumab 300 mg Q2W against placebo with respect to pre-bronchodilator FEV1 at Week 24 are as follows:

- Null hypothesis: $\Delta_{\text{FEV1_24_Dupi}} - \Delta_{\text{FEV1_24_Pbo}} = 0$
- Alternative hypothesis: $\Delta_{\text{FEV1_24_Dupi}} - \Delta_{\text{FEV1_24_Pbo}} \neq 0$

where $\Delta_{\text{FEV1_24_Dupi}}$ and $\Delta_{\text{FEV1_24_Pbo}}$ represent the mean absolute change from baseline in pre-bronchodilator FEV1 at Week 24 in the dupilumab and placebo groups, respectively.

1.3. Interim Analysis(es)

No interim analysis is planned.

1.4. Modifications from the Statistical Section in the Final Protocol

Only a single set of potentially clinically significant values (PCSV) tables will be provided for each applicable safety category (e.g., laboratory tests, electrocardiography, and vital signs). As the PCSV criteria defined in Section 14.3 are primarily defined in terms of changes from baseline, separate tables for patients in whom the PCSV criterion was normal or missing at baseline are not applicable.

Only listings required for the clinical study report will be produced.

In the definition of the on-treatment period for safety variables, mention of the date of patient last contact was removed; this text is not applicable as the date of patient last contact cannot be prior to the date of the last adverse event reported for an individual patient. In addition, the definition of the follow-up period for safety variables was modified to ensure a consistent reporting window for all patients.

1.5. Revision History for SAP Amendments

This is the original version of the SAP.

2. INVESTIGATION PLAN

2.1. Study Design

This phase 2, global, multicenter, randomized, double-blind, placebo-controlled, parallel-group study of dupilumab is designed to evaluate the efficacy and safety of dupilumab in adult and adolescent (≥ 12 years of age) patients with ABPA who meet modified ISHAM working group 2013 criteria for ABPA. Approximately 60 patients will be enrolled in the study. The study consists of 3 study periods:

[figure not shown]
- Screening period (4 weeks)
- Randomized treatment period (24-52 weeks)
- Post-treatment follow-up period (12 weeks)

Patients who meet the eligibility criteria will be randomized (1:1) to 1 of the following treatment groups:

- Dupilumab 300 mg, after a loading dose of 600 mg on Day 1, administered SC Q2W
- Matching placebo, administered SC Q2W

Randomization will be stratified by region (pooled country: Asia, Eastern Europe, Western Countries), chronic systemic corticosteroid use at screening (yes, no), and oral antifungal (OAF) use at screening (yes, no). Per protocol, patients on oral corticosteroids (OCS) must agree to switch to study required prednisone/prednisolone as their OCS at Visit 1 and use it per protocol for the duration of the study.

Rescue courses of systemic steroids for exacerbations, as determined by the investigators, will be permitted during the study. Patients will be required to continue all background asthma controller medications (inhaled corticosteroids [ICS]) with or without long-acting beta agonist (LABA), leukotriene receptor antagonist (LTRA), or long-acting muscarinic receptor antagonist (LAMA) without any changes in the dose or regimen during the study period. However, if 2 or more exacerbations occur during the treatment period, changes to background therapy (e.g., changes to background asthma controller medication or initiation of antifungal therapy) may be made at the investigator's discretion.

Patients who experience a severe respiratory exacerbation will have, as soon as possible, an unscheduled visit at the site for the collection of a blood sample for serum total IgE measurement.

[figure not shown]
For patients receiving OAF therapy during the treatment period, the dose and regimen of the OAF agent should remain stable until the end of the treatment period. However, antifungal discontinuation or modification to the dose or regimen is permitted for the following reasons: side effects, intolerance, or lack of efficacy (e.g., acute exacerbation) as determined by the investigator. Initiation of therapy with OAF agents is permitted if 2 or more exacerbations occur during the course of the study.

Upon completing the randomized treatment period, patients will continue their background therapy and enter a 12-week safety follow-up period. Adjustment of background asthma and ABPA medications will be allowed at the discretion of the investigator as clinically indicated during the post-treatment follow-up period.

Patients who withdraw from the study prematurely will have, at the time of their next regularly scheduled visit, an early termination visit. This early termination visit will consist of all assessments normally planned for the end of study (EOS) visit. To allow assessment of patient outcomes over the stipulated study period, patients who discontinue study treatment but continue in the study will be asked and encouraged to complete all applicable remaining study visits and participate in all safety follow-up assessments according to the visit schedule (see Section 14.2).

Presented below is the study flow diagram depicting the different periods of the study. Study assessments and procedures (including treatment administrations) are presented by study period and scheduled visit in the Schedule of Time and Events in Section 14.2.

Figure 1: Study Flow Diagram

Note: Upon implementation of protocol amendment 3, the treatment period for all participants will be a minimum of 24 weeks and a maximum of 52 weeks. The week of EOT and EOS will vary accordingly.

ABPA=allergic bronchopulmonary aspergillosis; D1=Day 1; EOS=end of study; EOT=end of treatment; Q2W=every 2 weeks; SC=subcutaneous.

2.2. Sample Size and Power Considerations

The power calculation for this study is based on a comparison between dupilumab 300 mg Q2W and placebo with regard to the primary efficacy endpoint of the absolute change from baseline in pre-bronchodilator FEV1 at Week 24. Assuming a 1:1 randomization ratio, a standard deviation (SD) for the change from baseline in pre-bronchodilator FEV1 at Week 24 of [REDACTED] in both groups, a 2-sided Type 1 error of 0.05, and a dropout rate of [REDACTED] by Week 24, with approximately 60 randomized patients (\approx 30 per group), the study will have approximately 96% power to detect a difference of [REDACTED] in the change from baseline in pre-bronchodilator FEV1 at Week 24 between the dupilumab and placebo groups. The power was calculated via a 2-sample t-test using [REDACTED] software.

[REDACTED]

[REDACTED]

[REDACTED]

[REDACTED]

[REDACTED]

3. ANALYSIS SETS

The following defines the sets of patients whose data will be used for statistical analysis.

3.1. Full Analysis Set

The full analysis set (FAS) includes all randomized patients. It is based on the treatment allocated (as randomized), regardless of whether the treatment kit was used or not.

3.2. Safety Analysis Set

The safety analysis set (SAF) includes all randomized patients who received any study drug; it is based on the treatment received (as treated). “As treated” is defined as follows:

- If a patient receives at least 1 dupilumab injection during the study, the patient will be assigned to the dupilumab 300 mg Q2W treatment group in all analyses on the SAF population, regardless of the treatment group to which the patient was randomized.
- If a patient receives only placebo injections during the study, the patient will be assigned to the Placebo group in all analyses on the SAF population, regardless of the treatment group to which the patient was randomized.

3.3. Pharmacokinetic Analysis Set

The Pharmacokinetic Analysis Set (PKAS) includes all randomized patients who received any study drug and who had at least one non-missing drug concentration result following the first dose of study drug. The PKAS is based on the treatment received rather than as randomized.

3.4. Immunogenicity Analysis Sets

3.4.1. Anti-drug Antibody Analysis Set

The Anti-drug Antibody (ADA) Analysis Set (AAS) includes all treated patients who received any amount of study drug (active or placebo) and who had at least one non-missing ADA result following the first dose of study drug. The ADA analysis set is based on the treatment received rather than as randomized.

3.4.2. Neutralizing Antibody Analysis Set

The Neutralizing Antibody (NAb) Analysis Set (NAS) includes all treated patients (active or placebo) that are included in the AAS analysis set and that tested negative at all ADA sampling times or tested positive at one or more post-dose ADA sampling times and had at least one non-missing post-dose NAb result (either imputed or analysis result). Samples that tested negative for ADA are not assayed in the NAb assay and the corresponding NAb results are imputed as negative and included as such in the NAS analysis set. Patients in the NAS with multiple post-dose ADA results which consist of both imputed NAb-negative result(s) for ADA negative samples and only missing NAb results for all ADA-positive result(s), are set to NAb negative. Patients in the NAS that have at least one post-dose positive NAb analysis result are set to NAb positive even if other NAb results are missing.

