## 11.3.4. Immunogenicity Analysis Sets

The ADA analysis set includes all patients who received any study drug and who had at least 1 non-missing ADA result following the first study dose.

The NAb analysis set includes all patients who received any study drug and who are negative in the ADA assay or with at least 1 non-missing result in the NAb assay (patients who are ADA-negative are set to negative in the NAb analysis set).

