## 11.4.6. Analysis of Immunogenicity Data

Immunogenicity will be characterized into ADA and NAb responses as described below:

- Pre-existing immunoreactivity, defined as a positive ADA assay response at baseline, with all post-dose ADA results negative, or a positive assay response at baseline, with all post-dose ADA assay responses less than 4-fold over baseline titer levels
- Treatment-emergent ADA response, defined as any post-dose positive ADA assay response when the baseline results are negative or missing
  - Treatment-emergent ADA response may be further characterized as persistent, transient, or indeterminate
- Treatment-boosted ADA response, defined as any post-dose positive ADA assay response that is 4-fold over baseline titer levels when baseline is positive in the ADA assay
- Maximum ADA Titer values
  - Low (titer <1,000)
  - Moderate  $(1,000 \le \text{titer} \le 10,000)$
  - High (titer >10,000)
- NAb status for samples that are positive in the ADA assay depending on the study

Listings of pre-existing, treatment-boosted, and treatment-emergent ADA responses, ADA titers, and NAb positivity presented by patient, time point, and dose cohort will be provided. Incidence of treatment-emergent ADA, persistent response, and NAb will be assessed as absolute occurrence (N) and percent of patients (%), grouped by study cohorts and ADA titer level.

Plots of drug concentrations will be examined and the influence of ADAs and NAbs on individual PK profiles evaluated. Assessment of impact of ADA and NAbs on safety and efficacy may be provided.

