10.6.2. Analysis of Immunogenicity Data

10.6.2.1. Analysis of ADA Data

The immunogenicity variables described in Section 10.6.1 will be summarized using descriptive statistics. Immunogenicity will be characterized per drug molecule by ADA status, ADA category, and maximum titer category observed in patients in the AAS analysis set. For samples confirmed as drug-specific ADA positive, but found negative at the lowest titer dilution, the lowest dilution in the titer assay is imputed.

The ADA status of each patient may be classified as one of the following:

- Positive
- Pre-existing - If the baseline sample is positive and all post-baseline ADA titers are reported as less than 4-fold the baseline titer value
- Negative - If all samples are found to be negative in the ADA assay

The ADA category of each positive patient is classified as:

- Treatment-boosted - A positive result at baseline in the ADA assay with at least one post-baseline titer result ≥ 4 -fold the baseline titer value
- Treatment-emergent - A negative result or missing result at baseline with at least one positive post-baseline result in the ADA assay. Patients that are treatment-emergent will be further sub-categorized as follows:
 - Persistent - A positive result in the ADA assay detected in at least 2 consecutive post-baseline samples separated by at least a 12-week post-baseline period [based on nominal sampling time], with no ADA-negative results in-between, regardless of any missing samples
 - Indeterminate - A positive result in the ADA assay at the last collection time point only, regardless of any missing samples
 - Transient - Not persistent or indeterminate, regardless of any missing samples

The maximum titer category of each patient is classified as:

- Low (titer $< 1,000$)
- Moderate ($1,000 \leq \text{titer} \leq 10,000$)
- High (titer $> 10,000$)

The following will be summarized by treatment group and ADA titer level:

- Number (n) and percent (%) of ADA-negative patients
- Number (n) and percent (%) of pre-existing patients
- Number (n) and percent (%) of treatment-emergent ADA positive patients
 - Number (n) and percent (%) of persistent treatment-emergent ADA positive patients
 - Number (n) and percent (%) of indeterminate treatment-emergent ADA positive patients
 - Number (n) and percent (%) of transient treatment-emergent ADA positive patients
- Number (n) and percent (%) of treatment-boosted ADA positive patients

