10.6.2.2. Analysis of NAb Data

The absolute occurrence (n) and percent (%) of patients with each NAb status in the NAS analysis set will be provided by treatment group. The NAb status is categorized as follows:

- Negative – Samples tested negative in the ADA assay, or samples positive in the ADA assay but tested negative in the NAb assay
- Positive – Samples tested positive in the NAb assay

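### SAP 3.4.2, read literally, leaves out of the NAb analysis set patients who are ADA-positive only at baseline, so a descriptive NAb percentage can be slightly too high

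*SAP*

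**What the plan says.** **NAb set in the SAP (3.4.2).** The parent set is the AAS, which requires at least one post-dose ADA result and ignores baseline status (SAP 3.4.1). From it, the NAS takes patients "that tested negative at all ADA sampling times or tested positive at one or more post-dose ADA sampling times", with a requirement for a non-missing post-dose NAb result, which may be imputed. On imputation: "Samples that tested negative for ADA are not assayed in the NAb assay and the corresponding NAb results are imputed as negative". On patient status: "Patients in the NAS that have at least one post-dose positive NAb analysis result are set to NAb positive".

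**NAb set in the protocol (11.3.4).** It takes treated patients "who are negative in the ADA assay or with at least 1 non-missing result in the NAb assay". The NAb result is not required to be post-dose.

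**The patient in question.** Protocol 11.4.6 counts as pre-existing immunoreactivity "a positive ADA assay response at baseline, with all post-dose ADA results negative". SAP 10.6.2.1 covers the same patient under the ADA status Pre-existing: "If the baseline sample is positive and all post-baseline ADA titers are reported as less than 4-fold the baseline titer value".

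**Reporting.** SAP 10.6.2.2 reports the number and percentage with each NAb status in the NAS by treatment group, and defines negative by sample: "Samples tested negative in the ADA assay, or samples positive in the ADA assay but tested negative in the NAb assay". SAP 5 tabulates patients excluded from each analysis set, with reasons. SAP 1.4, which lists departures from the protocol's statistical section, does not mention the NAb set.

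**The concern.** The two entry conditions do not cover every patient whose NAb status is known. Baseline is an ADA sampling time: the schedule of events has an ADA sample at Week 0, and footnote u requires collection before dosing. A patient who is positive there and negative afterwards fails the first condition because of the baseline sample, and fails the second because no post-dose sample is positive. The patient appears in the ADA table as pre-existing and is absent from the NAb table.

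The omission sits oddly with the rest of the section. SAP 3.4.2 keeps patients whose ADA-positive samples all lack a NAb result, provided they also have an ADA-negative sample, and sets them to NAb negative. Patients with uncertain status are kept, while one whose available post-dose results are all negative is dropped. No reason is given.

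At stake is the denominator of a descriptive immunogenicity percentage, plus an unlisted departure from the protocol's definition.

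**Working it through.** **No figure to reproduce.** Neither document states a NAb incidence or a NAS size, so the check is of the rule itself, followed by its effect under assumed counts.

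**Step 1: apply the rule to the pattern (baseline positive, all post-dose samples negative).**
- In the AAS? Yes, because there is a post-dose ADA result.
- Negative at every sampling time? No, baseline is positive.
- Positive at a post-dose time? No.
- Non-missing post-dose NAb result? Yes, imputed negative.
- Result: excluded from the NAS. If the patient were included, the status would be NAb negative.

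**Step 2: check that nothing depends on how the sentence is parsed.** The non-missing NAb requirement can attach to the second condition only or to both. I took baseline as negative, positive or missing, and each of the four post-dose sampling visits (Week 12, Week 24, EOT, EOS) as one of: ADA-negative; ADA-positive with NAb positive, negative or missing; or ADA missing. A missing baseline was not counted as positive. Both parsings give the same NAS. Exactly two kinds of AAS patient are left out:

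| Pattern excluded | NAb status under SAP 3.4.2 |
|---|---|
| Baseline ADA-positive, every available post-dose ADA result negative | Negative in every case |
| Every available post-dose ADA result positive, every corresponding NAb result missing | Unknown |

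The second exclusion is understandable, because the status cannot be determined. The first is the gap.

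**Step 3: compare with the protocol.** Protocol 9.2.5 sends ADA-positive samples to the NAb assay. The positive baseline sample is therefore assayed and, if its result is non-missing, Protocol 11.3.4 admits the patient.

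**Step 4: size.** Let N be the patients per arm who should be in the set, x the baseline-only positives, and k the NAb-positive patients. As written, the percentage is k/(N − x); with these patients kept as negative it is k/N. The ratio is N/(N − x).

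Inputs: N = 30 (Protocol 7.1 plans about 30 per arm; I assume all of them contribute). The values x = 1 to 3 and k = 1 to 3 are assumptions, as the documents give neither.

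| k | k/30 (patients kept) | x = 1: k/29 | x = 2: k/28 | x = 3: k/27 |
|---|---|---|---|---|
| 1 | 3.33% | 3.45% | 3.57% | 3.70% |
| 2 | 6.67% | 6.90% | 7.14% | 7.41% |
| 3 | 10.00% | 10.34% | 10.71% | 11.11% |

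Ratios: 30/29 = 1.034, 30/28 = 1.071, 30/27 = 1.111. The absolute difference runs from 0.11 to 1.11 percentage points. It is zero if k = 0 or x = 0.

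**The case against.** **The first condition may be meant to cover post-dose samples only.** If so, there is no gap. However, the same sentence writes post-dose in the second condition and omits it in the first, and SAP 10.6.2.1 reserves the ADA status Negative for patients with all samples negative. The wording should not be left to the programmer's judgment.

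**The report will show the exclusion.** SAP 5 gives NAS exclusions by arm and reason, the ADA table counts the patient as pre-existing, and the NAb-positive count is reported alongside the percentage. A careful reader could rebuild the denominator. This stands as mitigation, but it does not correct the percentage that is printed.

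**The direction depends on which samples decide status.** SAP 10.6.2.2 defines NAb positive by sample, with no post-dose limit. If a positive baseline NAb result counted, the exclusion could lower incidence relative to the protocol's set: with one other positive patient, 1/29 (3.45%) against 2/30 (6.67%). SAP 3.4.2 assigns a positive status on post-dose results, so I use that basis, but the SAP should state it.

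**Two stronger readings are tempting.** A reader might infer that the NAS rules as a whole can only push NAb incidence up. They do not: the rule that sets some patients with missing NAb results to negative can push it down, and the net direction is not fixed. A reader might also infer that secondary endpoint 11 is biased. That endpoint (Protocol 4.1.2) names treatment-emergent ADA, not NAb. The affected patient is pre-existing and stays in the AAS, so the endpoint's incidence is untouched.

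**Conclusion.** The gap is real but small. As written, SAP 3.4.2 excludes a foreseen type of patient whose post-dose NAb status is negative under its own imputation rule, and it narrows the protocol's set without saying so in SAP 1.4.

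The effect is conditional. The NAb percentage in an arm is overstated by this gap only if that arm has at least one baseline-only positive and at least one NAb-positive patient, and only when status is judged on post-dose samples. The documents do not show that either count will be above zero, so they do not support saying that NAb incidence is overstated in this trial. Over the assumed range the shift is about 0.1 to 1.1 percentage points, in arms where one patient is worth 3.3 points (1/30). The NAb table is descriptive, and no test or efficacy result rests on it. This is a minor wording correction.

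**What to change.** 1. In SAP 3.4.2, reword the first condition to: *negative at all post-dose ADA sampling times, regardless of the baseline ADA result*. Baseline-only positives then enter the NAS as NAb negative.
2. In SAP 3.4.2 or 10.6.2.2, state that a patient's NAb status is based on post-dose samples.
3. In SAP 1.4, record any difference from Protocol 11.3.4 that remains. One is the patient whose post-dose ADA results are all positive with all NAb results missing, but who has a baseline NAb result: the protocol's wording admits this patient and the SAP's does not.

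If the exclusion is intended, the alternative is to keep it and give the reason in SAP 1.4.

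The cost is one phrase, one clarifying sentence and one entry in SAP 1.4, plus a matching change to the program that flags the NAS. No new data are needed.

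### SAP 3.4.2 counts some patients with unknown NAb status as NAb negative, which can lower but never raise NAb incidence, and SAP 1.4 does not list this as a change from the protocol

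*SAP*

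**What the plan says.** The SAP lets an ADA-positive patient into the NAb analysis set if the patient "had at least one non-missing post-dose NAb result (either imputed or analysis result" (SAP 3.4.2). The imputed results arise as follows: "Samples that tested negative for ADA are not assayed in the NAb assay and the corresponding NAb results are imputed as negative". A patient with such an imputed negative at one visit and no NAb result on any ADA-positive sample is therefore in the set, and the same section fixes the status: patients with "only missing NAb results for all ADA-positive result(s), are set to NAb negative". In the other direction, patients with "at least one post-dose positive NAb analysis result are set to NAb positive even if other NAb results are missing".

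The results go into a table: the number and percentage of "patients with each NAb status in the NAS analysis set will be provided by treatment group" (SAP 10.6.2.2). Only two statuses exist there, negative and positive. Negative covers ADA-negative samples and "samples positive in the ADA assay but tested negative in the NAb assay".

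Protocol 11.3.4 defines the set differently. It takes treated patients who are "negative in the ADA assay or with at least 1 non-missing result in the NAb assay", and adds that ADA-negative patients are set to negative. It mentions no imputed result for a patient who is ADA positive. SAP 1.4, which lists departures from the protocol's statistical section, is silent on this.

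**The concern.** Only ADA-positive samples go into the NAb assay (Protocol 9.2.5, SAP 10.6.1). When all of a patient's ADA-positive samples lack a NAb result, nothing has been measured that bears on whether those antibodies neutralize. The rule fills the gap with a negative carried over from a visit at which no antibody was found and no NAb assay was run. An unknown status is thus entered as a known negative, in both the negative count and the denominator.

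The rule is also uneven. A patient who is ADA positive at every post-dose sample, with every NAb result missing, has neither an assayed nor an imputed result and drops out of the set. Give the same patient one ADA-negative post-dose sample and the patient becomes NAb negative. Neither has a NAb result on an ADA-positive sample.

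At stake is one descriptive figure, the incidence of NAb by arm, which Protocol 11.4.6 says will be assessed. The optional individual concentration plots by NAb status (SAP 10.6.3.1) would carry the same label.

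**Working it through.** No figure in the documents depends on this rule, so there is nothing to reproduce. The check is a reading of the passages followed by simple bounds.

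**Step 1. Classify three patients under each text.** Protocol Table 1 schedules post-dose ADA samples at weeks 12 and 24, EOT and EOS, so mixed patterns are possible.

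| Post-dose pattern | Protocol 11.3.4 (plain reading) | SAP 3.4.2 |
|---|---|---|
| All samples ADA negative | In the set, negative | In the set, negative |
| ADA positive at every sample, every NAb result missing | Not in the set | Not in the set |
| Some ADA negative, some ADA positive, NAb missing on all ADA-positive samples | Not in the set | In the set, negative |

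The texts part only in the third row. What brings that patient in is the SAP's allowance for an imputed result.

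**Step 2. Inputs for the size.**
- n: patients in the NAb set in one arm, under the SAP rule. Assumed 30, from the planned 30 or so per arm (Protocol 7.1).
- x: patients observed NAb positive. Not given; assumed 0 to 3.
- m: patients with the third-row pattern. Not given; assumed 0 to 3.
- k: how many of those m are truly positive, between 0 and m. Unknown.
- Second-row patients are taken as zero in this illustration.

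**Step 3. Formulas.**
- SAP rule: x/n.
- Affected patients excluded: x/(n − m).
- Incidence if their status were known: (x + k)/n, which lies between x/n and (x + m)/n.

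Since k cannot be negative, x/n is never above (x + k)/n. The shortfall is k/n, at most m/n. For one truly positive patient it is 1/30 = 3.3 percentage points.

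**Step 4. Selected results for n = 30.**

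| x | m | SAP rule | Excluded | Upper bound |
|---|---|---|---|---|
| 1 | 0 | 3.3% | 3.3% | 3.3% |
| 0 | 1 | 0.0% | 0.0% | 3.3% |
| 1 | 1 | 3.3% | 3.4% | 6.7% |
| 1 | 2 | 3.3% | 3.6% | 10.0% |
| 2 | 2 | 6.7% | 7.1% | 13.3% |

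**Step 5. What exclusion alone achieves.** Take x = 1, m = 1 and suppose the affected patient is truly positive. Known incidence would be 2/30 = 6.7%. The SAP rule gives 1/30 = 3.3% and exclusion gives 1/29 = 3.4%. Exclusion recovers about 0.1 of the 3.3 points, because it takes out an ADA-positive patient while every ADA-negative patient stays in the denominator. Bounds show the uncertainty; exclusion mostly hides it.

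**The case against.** The strongest reply is that this is an explicit, prespecified convention for a descriptive summary with no test attached, in a situation the plan means to avoid: ADA-positive samples are to be assayed for NAb, so the rule bites only if that fails for every such sample of a patient who also has an ADA-negative one. The two patients contrasted under the concern do differ in observed data, and the SAP's default of a separate missing category (Section 4) applies only where nothing else is stated. All of that is fair, and it keeps the point small. It does not turn an unmeasured status into a measured one, nor explain the unlisted departure from the protocol.

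Four stronger readings are tempting, and the documents support none of them.
- *A reader might infer that NAb incidence is in fact understated.* That needs at least one affected patient who is truly positive. The documents give neither number.
- *A reader might infer that an affected patient cannot be NAb negative.* SAP 10.6.2.2 allows for ADA-positive samples that test NAb negative, so the rule may classify such a patient correctly.
- *A reader might take 3.3 points per patient as the expected distortion.* It is the worst case for one patient in an assumed arm of 30.
- *A reader might infer that the safety and efficacy displays are biased too.* SAP 10.6.3.2 lists ADA-positive, titer and NAb-positive categories. An affected patient is absent from the NAb-positive group under the present rule and under the fix alike.

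One could also defend the SAP by reading the protocol's ADA-negative condition sample by sample. Its wording is about patients, and its parenthesis sets ADA-negative patients to negative, so the plain reading stands.

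**Conclusion.** The point holds as a minor one. SAP 3.4.2 enters an unknown NAb status as a known negative, differs from the plain reading of Protocol 11.3.4, and is not listed in SAP 1.4. Any error goes one way: NAb incidence can come out too low and cannot come out too high because of this rule.

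The size is unknown and may be nil. With no affected patients nothing changes; if all affected patients are truly negative, the reported incidence is right. The 3.3-point ceiling per patient rests on the assumed 30 per arm. The primary FEV1 analysis is not involved.

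**What to change.** In SAP 3.4.2, replace the sentence that sets these patients to negative. Any patient with at least one ADA-positive post-dose sample and no NAb result on any ADA-positive sample becomes NAb not determined. This covers both the mixed pattern and the patient who is ADA positive throughout, so the uneven treatment goes as well.

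In SAP 10.6.2.2, add a row with the number of such patients (m) by arm, and report NAb incidence with the bounds x/n to (x + m)/n, where n includes them.

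If the sponsor prefers to keep the present rule, SAP 1.4 should list it as a change from Protocol 11.3.4, and the table should still show m and the bounds.

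The cost is a reworded sentence, one extra table row and a slightly less definite incidence figure. If m is zero, the bounds coincide and the row shows that the question did not arise.
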